9.4 VITAL SIGNS

Measurement of vital signs will include assessment of blood pressure, respiratory rate, pulse, and oral temperature. The visit-specific average value of the multiple measurements at these scheduled study visits will be calculated and used in the summary table.

For each vital sign parameter, the observed value and change from Baseline value will be summarized using descriptive statistics by study visit and treatment group.

All vital signs data will be presented in the patient listings.

9.5 ECG

Electrocardiograms (12-lead ECGs) will be performed as specified in [Table 1](#). The following ECG parameters will be recorded: heart rate (bpm), RR interval (msecs), PR interval (msecs), QRS interval (msecs), QT interval (msecs), and corrected QT (QTc) intervals (msecs). QT will be corrected for heart rate using Fridericia’s (QTcF) interval.

For each ECG parameter, the observed value and change from Baseline value will be summarized using descriptive statistics by study visit and treatment group for all patients in the safety population.

In addition, count and percentage of patients with outlying QTcF values (i.e., value >450, >480 or >500 msec, increase from Baseline value of >30 or >60 msec) based on ICH Guidance E14^[4] will be presented by study visit and treatment group.

All ECG data will be included in patient listings.

9.6 PHYSICAL EXAMINATION

Complete physical examinations will be performed at Baseline Day 1, Week 48, Week 84/EOS visit, and 2 Week Follow-up visit if evaluation at Week 84/EOS is abnormal. Complete physical examinations will include a minimum of a review of the patient’s general appearance, head, eyes, ears, nose, and throat, neck, heart, lungs, abdomen, back and extremities, skin, and general neurological system. Symptom-oriented physical examinations including weight will be performed at all other time points as well and as clinically indicated.

1003157

Lexicon Pharmaceuticals, Inc.

LX1606.302

Final V1.0

Statistical Analysis Plan

The complete physical examination result will be reported as “Normal”, “Abnormal, Not Clinically Significant”, or “Abnormal, Clinically Significant” with respect to relevant abnormalities by the Investigator. The number and percentage of patients with abnormal physical examination results will be summarized by body system and treatment group over time. The symptom-oriented physical examination result will be reported as “Clinically Significant Change since Previous Exam, Yes”, or “Clinically Significant Change since Previous Exam, No”. The number and percentage of patients with each result will be summarized by treatment group over time.

Physical examination results will be also presented in a data listing.

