4.8 STUDY PROCEDURES

A schedule of study events is provided in [Table 1](#).

Statistical Analysis Plan

Table 1 Schedule of Events

Procedure	Extension Period								2-Week Follow-up ⁴
	Baseline Day 1 ¹	Week 12	Week 24	Week 36	Week 48	Week 60	Week 72	Week 84 / EOS	
Tolerance (days)	NA	± 5	± 5	± 5	± 5	± 5	± 5	± 5	± 5
Inclusion/Exclusion criteria	X								
Medical history	X								
Physical examination incl. weight	X	X ³	X ³	X ³	X	X ³	X ³	X	X ⁵
Urine pregnancy test ²	X	X	X	X	X	X	X	X	X
Hematology, Blood chemistry	X	X	X	X	X	X	X	X	X ⁵
Urinalysis	X				X			X	X ⁵
Chromogranin A	X				X			X	
Vital signs	X	X	X	X	X	X	X	X	X
ECG	X				X			X	X ⁵
Subjective Global Assessment	X	X	X	X	X	X	X	X	X
EORTC QLQ-C30 & GLNET21	X		X		X		X	X	
Sleep and Depression Assessment	X	X	X	X	X	X	X	X	X
Plasma 5-HIAA	X	X	X	X	X	X	X	X	X
Dispensation of LX1606	X	X	X	X	X	X	X		
Concomitant medications	X	X	X	X	X	X	X	X	X
Adverse events	X	X	X	X	X	X	X	X	X

¹Eligibility will be determined at last visit of the original protocol; Day 1 will replace the next scheduled visit in the original protocol schedule. Visits should coincide with LAR injections for those patients receiving SSA therapy. ²Females of child-bearing potential only. ³Brief physical examination only (symptom-oriented, including weight). ⁴Visit to be performed for subjects who withdraw early and will not return for a 2-week follow-up visit; in all other cases the EOS visit should be performed followed by the follow-up visit 2 weeks postdose. ⁵To be performed only if evaluation at Week 84/EOS is abnormal.

Statistical Analysis Plan

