5.3 SAFETY ENDPOINTS

Safety endpoints are as follows:

- Incidence of TEAEs, suspected adverse reaction, adverse events (AEs) leading to discontinuation from the study, serious AEs (SAEs), deaths, and AEs of special interest
- Actual and change from Baseline in clinical laboratory results
- Actual and change from Baseline in vital signs results
- Actual and change from Baseline in physical examinations
- Actual and change from Baseline in ECG findings

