9.3 LABORATORY EVALUATIONS

Laboratory results will be reported in standard international system (SI) of units in all TLFs. Clinical laboratory test results (hematology, chemistry, urinalysis, and CgA) and their changes from Baseline value will be summarized by treatment group and analysis visit using descriptive statistics. The laboratory test results (hematology, chemistry, and urinalysis) will be reported as "High", "Low", or "Normal" with respect to relevant reference ranges. A shift table comparing the laboratory test results over the analysis visits to Baseline measure will be presented.

1003157

Lexicon Pharmaceuticals, Inc.

LX1606.302

Final V1.0

Statistical Analysis Plan

All laboratory data will be listed. The laboratory results falling out of the normal range will be marked as “High” or “Low” in the listings. Pregnancy results will be presented in patient listings only.

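### Section 5.3 makes change from Baseline in physical examinations a safety endpoint, but Section 9.6 specifies no within-patient comparison with Day 1

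*SAP*

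**What the plan says.** Section 5.3 of the SAP includes among the safety endpoints "Actual and change from Baseline in physical examinations". Section 7.2.1 fixes Baseline as Day 1 of this study.

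Section 9.6 uses two kinds of examination:

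- **Complete examination.** "Complete physical examinations will be performed at Baseline Day 1, Week 48, Week 84/EOS visit", and at follow-up if the Week 84/EOS result is abnormal. Each result is graded normal, abnormal not clinically significant (NCS), or abnormal clinically significant (CS). The planned summary is: "The number and percentage of patients with abnormal physical examination results will be summarized by body system and treatment group over time".
- **Brief, symptom-oriented examination.** Table 1 places this at Weeks 12, 24, 36, 60 and 72. The result is either "Clinically Significant Change since Previous Exam, Yes" or the corresponding No. The planned summary is: "The number and percentage of patients with each result will be summarized by treatment group over time".

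Weight belongs to the examination. The Table 1 row reads "Physical examination incl. weight", and its footnote for the brief visits also includes weight. The vital-signs list in Section 9.4 does not name it: "Measurement of vital signs will include assessment of blood pressure, respiratory rate, pulse, and oral temperature".

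For laboratory data, Section 9.3 does plan a patient-level comparison with Day 1: "A shift table comparing the laboratory test results over the analysis visits to Baseline measure will be presented".

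**The concern.** The endpoint is a change from Day 1, but neither summary in Section 9.6 is defined as one. The complete-examination table gives a percentage at each visit without linking a patient's later result to that patient's Day 1 result. The brief-examination table refers to the preceding examination, and its Yes has no direction, so an improvement can count as well as a worsening. Sections 9.3, 9.4 and 9.5 each state a comparison with Baseline for laboratory values, vital signs and ECG. Among the items that Section 5.3 lists with a change from Baseline, physical examination is the only one without such a comparison in its analysis section.

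The primary objective is long-term safety and tolerability. A reader of the report will want to know how many patients acquired a new significant examination finding while on treatment, and the tables as specified do not give that number.

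**Working it through.** **Counting the visits (Table 1).** There are seven scheduled on-treatment examinations after Day 1. Five are brief (Weeks 12, 24, 36, 60, 72) and two are complete (Weeks 48 and 84/EOS).

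**Tracing a finding through the recording rules of Section 9.6.** Each row is one patient with one finding that persists once present.

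| Finding | W12 | W24 | W36 | W48 | W60 | W72 | W84 |
|---|---|---|---|---|---|---|---|
| Present on Day 1, stable | No | No | No | Abnormal | No | No | Abnormal |
| New at Week 12 | Yes | No | No | Abnormal | No | No | Abnormal |
| New, first seen at Week 48 | No | No | No | Abnormal | No | No | Abnormal |
| New at Week 60 | No | No | No | Normal | Yes | No | Abnormal |

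From Week 24 on, the second patient contributes the same entries as the first. The third matches the first at all seven visits and never yields a Yes, because Week 48 uses the other kind of examination. These patients differ from the first on Day 1, but a table of visit percentages does not carry that link forward.

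**Offsetting within a body system (assumed numbers).** Of 100 patients, 30 are abnormal on Day 1, 10 of these resolve, and 10 of the 70 others become abnormal.

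- Abnormal at the later visit: 30 − 10 + 10 = 30, so the table shows 30% both times.
- Newly abnormal among those normal on Day 1: 10/70 = 14%.

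**What the complete-examination table can show (assumed numbers).** Suppose 10% of patients develop a persistent new finding, with onset uniform over Weeks 0 to 72 and no resolution.

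- Rise over Day 1 at Week 48: 10% × 48/72 = 6.7 percentage points.
- Rise over Day 1 at Week 84: 10 percentage points.

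So a net increase is visible at group level. What is lost is the split into new, persisting and resolved findings.

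**Denominator.** Section 7.1 takes the treatment-group total as the default, while Section 14.2.5.2 takes patients with an observation. A comparison of visit percentages depends on which is used once patients leave, so any Day 1 comparison should state its own denominator.

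**The case against.** The strongest reply is that a Baseline comparison is already there. Day 1 is one of the complete-examination visits, so an over-time table naturally includes it, and the group percentages can be read against it. At Week 12 the previous examination is normally the Day 1 examination. Cancellation stays hidden only if it occurs within the same body system. All results are listed, adverse events are summarised per patient by organ class and preferred term, and the safety objectives in Section 3.3 do not list physical examination among the changes from Baseline. The table shells are attachments that are not shown and might contain a shift layout. All of this stands and limits the weight of the point. It does not supply the within-patient change that Section 5.3 names.

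Three stronger readings are tempting, and the documents do not support them:

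- *Persisting new findings disappear.* They are counted once as Yes if first seen at a brief examination, and appear as abnormal at Week 48 and/or Week 84/EOS.
- *The brief-examination table understates abnormality several-fold.* Under the uniform-onset assumption its rate is 10% × 12/72 = 1.67% per interval, against 10% cumulative. But these are different quantities: the item is worded as change since the previous examination, and a constant interval rate is then the correct result.
- *Weight goes unsummarised.* Section 7.1 makes descriptive statistics the default for continuous variables, and Section 7.5 has safety data summarised by study week in general, which may cover weight. It is only not named in Section 9.4 or in the summaries of Section 9.6.

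**Conclusion.** The point holds in a limited form. Section 5.3 names a change from Baseline that Section 9.6 does not specify at patient level. The planned tables support a group-level comparison with Day 1 at Weeks 48 and 84/EOS. They do not separate newly abnormal patients from those abnormal at entry, and the brief examinations measure interval change rather than the endpoint.

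The documents give no rate of examination findings, so the size cannot be estimated for this trial. The 30%/30% against 14% example shows only how the loss arises, and it rests on exact cancellation within one body system. The practical impact is modest: this is descriptive, open-label reporting, no decision rule depends on it, and the listings and adverse-event tables provide partial cover. The change is still worth making, because it delivers a stated safety endpoint at almost no cost.

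**What to change.** In Section 9.6:

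1. Add a shift table by body system and treatment group from Day 1 to Week 48 and from Day 1 to Week 84/EOS, with the three existing grades (normal, abnormal NCS, abnormal CS). Give the number newly abnormal CS, with patients examined at both visits who were not CS on Day 1 as the denominator.
2. State that the brief-examination result is interval change only and does not serve as the change-from-Baseline endpoint. A cumulative count of any Yes would not repair this, because it would include improvements and miss findings first seen at Week 48.
3. Name body weight, actual and change from Baseline by visit, among the summarised numeric safety parameters. This is the lesser item.

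If the sponsor does not want the shift table, Section 5.3 should be reworded to agree with Section 9.6.

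The cost is one or two extra descriptive tables from data already collected, with no new assessments.

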9.7 QUALITY OF SLEEP

Quality of sleep will be evaluated at each study visit. Patients will be asked to respond to the following question, “Since your last visit, how many times a night (on average) do you wake up due to your carcinoid syndrome symptoms?” based on the following scale 0, 1, 2, 3, 4, >4. Results will be presented in a data listing.

10 DSMB

An independent DSMB will review interim safety data on a quarterly basis and provide its recommendations to the Sponsor on whether to continue the study or to terminate the study. Appropriate procedures will be detailed in a DSMB charter that defines accessibility and disclosure of the interim safety results.

11 INTERIM ANALYSES

The study may be analyzed and reported in multiple phases. The first report will summarize data obtained from all patients providing information up to a specified data cut-off point. The following reports will update the initial report by including data from the remaining portion of the study. The first reporting of the data may be taken as an interim analysis in terms of the procedural efforts needed to summarize these data, but it will not serve as a means to modify the analysis/study conduct.

12 CHANGE FROM ANALYSIS PLANNED IN PROTOCOL

There are no changes from the analysis planned in the protocol.

14 PROGRAMMING CONSIDERATIONS

The following conventions will hold for programming of outputs:

- SAS (SAS Institute, Cary, NC) Version 9.3 or higher will be used for programming and production
- The format of the table shells will be followed as closely as possible; however, in the course of programming and familiarization with the database, some changes may become necessary. All changes will be documented. Major changes will be documented through a formal amendment to this document.
- Patients in this study will be identified as “Patients.”
- Descriptive statistics will be displayed in the following order:

n
Mean
SD
Median
Min, Max

1003157

Lexicon Pharmaceuticals, Inc.

LX1606.302

Final V1.0

Statistical Analysis Plan

- **Decimal places:** For summary statistics, the minimum and maximum will be reported with the same number of decimal places as the collected measure, the mean, LS mean (if applicable) and median will have 1 more decimal place than the measure collected, and the standard deviation and CI will have 2 more decimal places than the collected measure. For frequency distributions, percentages will be reported to 1 decimal place. For p-values, 3 decimal places will be reported with the following rules:
 - If $p\text{-value} < 0.001$, then use “ $p < 0.001$ ”
 - If $0.001 \leq p\text{-value} \leq 0.05$, then use “ $p = x.xxx$ ”
 - If $0.05 < p\text{-value} \leq 0.999$, then use “ $p = x.xx$ ”
 - If $p\text{-value} > 0.999$, then use “ $p > 0.999$ ”
- Unless otherwise noted, the denominator for percentages is the number of patients in the applicable analysis population and treatment group.
- If the frequency for a particular table cell is zero, then “0”, properly aligned, will be displayed (i.e., “0 (0.0%)” will not be displayed.)
- **Non-numeric values:** where variables are recorded using $<$ (e.g., “ <10 ” or “ ≤ 10 ”) the numeric portion of the result divided by 2 will be used (e.g., <10 and ≤ 10 becomes 5) for summary; where variables are recorded using $>$ (e.g., “ >10 ” or “ ≥ 10 ”) the numeric portion of the result will be used (e.g., >10 and ≥ 10 become 10) for summary; the actual recorded results, (e.g., “ <10 ” or “ >10 ”) will appear in listings.

14.1 GENERAL CONSIDERATIONS

The following conventions will be used.

- Each output will be stored in a separate file.
- Output files will be delivered in rich-text file format.
- Numbering of TLFs will follow ICH E3 guidance^[5]

14.2 TABLE, LISTING, AND FIGURE FORMAT

14.2.1 General

- All TLFs will be produced in landscape format, unless otherwise specified.

1003157

Lexicon Pharmaceuticals, Inc.

LX1606.302

Final V1.0

Statistical Analysis Plan

- All TLFs will be produced using the Courier New font, size 8
- The data displays for all TLFs will have a 1-inch binding margin on top of a landscape oriented page and a minimum 1-inch margin on the other 3 sides.
- Headers and footers for figures will be in Courier New font, size 8.
- Legends will be used for all figures with more than 1 variable, group, or item displayed.
- TLFs will be in black and white (no color), unless otherwise specified
- Specialized text styles, such as bolding, italics, borders, shading, and superscripted and subscripted text, will not be used in the TLFs, unless otherwise specified. On some occasions, superscripts 1, 2, or 3 may be used (see below).
- Only standard keyboard characters will be used in the TLFs. Special characters, such as non-printable control characters, printer-specific, or font-specific characters, will not be used. Hexadecimal-derived characters will be used, where possible, if they are appropriate to help display math symbols (e.g., μ). Certain subscripts and superscripts (e.g., cm^2 , C_{max}) will be employed on a case-by-case basis.
- Mixed case will be used for all titles, footnotes, column headers, and programmer-supplied formats, as appropriate.

14.2.2 Headers and Footers

- All output should have the following header at the top left of each page:

```
<Lexicon Pharmaceuticals, Inc.>  
Protocol LX1606.302  
Draft/Final Run <date>
```
- All output should have Page n of N at the top or bottom right corner of each page. TLFs should be internally paginated in relation to the total length (i.e., the page number should appear sequentially as page n of N, where N is the total number of pages in the table).
- The date (date output was generated) should appear along with program name and location as the last footer on each page.

1003157

Lexicon Pharmaceuticals, Inc.

LX1606.302

Final V1.0

Statistical Analysis Plan

14.2.3 Display Titles

- All TLFs should be identified by the designation and a numeral. (i.e., Table 14.1.1). ICH E3^[5] numbering is strongly recommended but Sponsor preferences should be obtained prior to final determination. A decimal system (x.y and x.y.z) should be used to identify TLFs with related contents. The title is centered. The analysis set should be identified on the line immediately following the title. The title and table designation are single spaced. A solid line spanning the margins will separate the display titles from the column headers. There will be 1 blank line between the last title and the solid line.

Table x.y.z
First Line of Title
Second Line of Title if Needed
ITT Analysis Set

14.2.4 Column Headers

- Column headings should be displayed immediately below the solid line described above in initial upper-case characters.
- In the case of efficacy tables, the variable (or characteristic) column will be on the far left followed by the treatment group columns and total column (if applicable). P-values may be presented under the total column or in separate p-value column (if applicable). Within-treatment comparisons may have p-values presented in a row beneath the summary statistics for that treatment.
- For numeric variables, include “unit” in column or row heading when appropriate.
- Analysis set sizes will be presented for each treatment group in the column heading as (N = xx) (or in the row headings if applicable). This is distinct from the ‘n’ used for the descriptive statistics representing the number of patients in the analysis set.
- The order of treatments in the tables and listings will be lowest dose first then higher doses, followed by a total column (if applicable).

14.2.5 Body of the Data Display

14.2.5.1 General Conventions

Data in columns of a table or listing should be formatted as follows:

1003157

Lexicon Pharmaceuticals, Inc.

LX1606.302

Final V1.0

Statistical Analysis Plan

- alphanumeric values are left-justified;
- whole numbers (e.g., counts) are right-justified; and
- numbers containing fractional portions are decimal aligned.

14.2.5.2 Table Conventions

- Units will be included where available
- If the categories of a parameter are ordered, then all categories between the maximum and minimum category should be presented in the table, even if $n = 0$ for all treatment groups in a given category that is between the minimum and maximum level for that parameter. For example, the frequency distribution for symptom severity would appear as:

Severity Rating	N
severe	0
moderate	8
mild	3

Where percentages are presented in these tables, 0 percentage will not be presented and so any counts of 0 will be presented as 0 and not as 0 (0%).

- If the categories are not ordered (e.g., Medical History, etc.), then only those categories for which there is at least 1 patient represented in 1 or more groups should be included.
- An Unknown or Missing category should be added to any parameter for which information is not available for 1 or more patients.
- Unless otherwise specified, the estimated mean and median for a set of values should be printed out to 1 more significant digit than the original values, and standard deviations should be printed out to 2 more significant digits than the original values. The minimum and maximum should report the same significant digits as the original values. For example, for systolic blood pressure:

N	XX
Mean	XXX.X

1003157

Lexicon Pharmaceuticals, Inc.

LX1606.302

Final V1.0

Statistical Analysis Plan

SD	X.XX
Median	XXX.X
Min, Max	XXX, XXX

- Percentage values should be printed to 1 decimal place, in parentheses with no spaces, 1 space after the count (e.g., 7 (12.8), 13 (5.4)). Predetermine how to display values that round down to 0.0. A common convention is to display as '< 0.1', or as appropriate with additional decimal places. Unless otherwise noted, for all percentages, the number of patients in the analysis set for the treatment group who have an observation will be the denominator. Percentages after 0 counts should not be displayed and percentages equating to 100% should be presented as 100, without any decimal places.
- Tabular display of data for medical history, prior / concomitant medications, and all tabular displays of AE data should be presented by the body system, treatment class, or SOC alphabetically, assuming all terms are coded. Within the body system, drug class and SOC, medical history (by PT), drugs (by ATC1 code), and AEs (by PT) should be displayed with the highest occurrence in the total column in decreasing order. If incidence for more than 1 term is identical, they should then be sorted alphabetically. Missing descriptive statistics or p-values which cannot be estimated should be reported as “-”.
- The percentage of patients is normally calculated as a proportion of the number of patients assessed in the relevant treatment group (or overall) for the analysis set presented. However, careful consideration is required in many instances due to the complicated nature of selecting the denominator, usually the appropriate number of patients exposed. Describe details of this in footnotes or programming notes.
- For categorical summaries (number and percentage of patients) where a patient can be included in more than 1 category, describe in a footnote or programming note if the patient should be included in the summary statistics for all relevant categories or just 1 category and the criteria for selecting the criteria.
- Where a category with a subheading (such as SOC) has to be split over more than 1 page, output the subheading followed by “(cont)” at the top of each subsequent page. The overall summary statistics for the subheading should only be output on the first relevant page.

1003157

Lexicon Pharmaceuticals, Inc.

LX1606.302

Final V1.0

Statistical Analysis Plan

